2.7.2 Statistical hypothesis, model, and method of analysis

The overall response rate (ORR, PR plus CR) and its two sided exact binomial 95% confidence interval will be provided for each patient group. The number and percentage of patients for different categories of overall response (e.g., for solid tumor - CR, PR, SD, PD, and NE) will be presented. These analyses will be performed with all solid tumor types combined and separately for each hematological tumor type. For tumor types that have ten (10) or more patients (within the solid tumors), separate summaries will be performed by the tumor type. In the event that there are fewer than 4 patients for a hematological tumor type, only listing will be provided for that tumor type. Additionally, the above analysis will also be repeated for overall response rate by 12 weeks and 18 weeks.

Components of tumor assessments (target lesion response, non-target lesion response, new lesion [yes/no]) will be listed. In addition, Cancer Antigen-125 (CA-125) in the assessment of ovarian cancer response, or Prostate-specific antigen (PSA) in the assessment of prostate cancer response will also be listed.

PFS, TTP and TTR will be summarized and graphed using the Kaplan-Meier product-limit method for each patient group. The estimates of the 25th, median, 75th percentiles of the PFS and their 95% confidence intervals will be provided, if applicable. Analyses will be based on

all tumor types combined. For tumor types, separate summaries will be performed by the tumor type.

DOR will be summarized using the Kaplan-Meier method and the median response presented along with 95% confidence interval only if there are sufficient numbers of events, otherwise, only listing of DOR will be provided. Analyses will be based all tumor types combined.

Additionally, a swimmer plot depicting time to onset and duration of response per RECIST 1.1 based on local radiology review will be presented.

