Secondary	Assess ORR by RECIST 1.1 in solid tumors and by the Revised Response Criteria for Malignant Lymphoma (Cheson et al 2007) in lymphoma TTR, DoR, TTP, PFS/ rate at 1 and 2 years Safety incidence and severity of adverse events (AEs) and serious adverse events (SAEs) including changes in laboratory parameters, vital signs and ECGs Tolerability: Dose interruptions, reductions and dose intensity.	Refer to Section 10.5 . To assess Overall Response (OR) of Partial Response (PR) or Complete Response (CR) based on local investigator assessment. Time to response (TTR) is defined as the time from the date of first dose to the date of first documented response of CR or PR. The duration of response (DOR) applies only to patients whose best response was PR or CR. The duration of response is defined as the time from the first documented response to the date first documented disease progression or relapse or death due to any cause. The duration of response will be summarized descriptively for each tumor cohort. Time to progression (TTP) is defined as the time from the date of first dose to the date of first documented disease progression or relapse. Progression free survival (PFS) is defined as the time from the date of first dose to the date of first documented disease progression or relapse or death due to any cause.

4 Study design

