The duration of response (DOR) applies only to patients whose best response was PR or CR. For patients with solid tumors the assessment criteria will be RECIST 1.1 and will include responses of CR and/or PR. For lymphoma the Revised Response Criteria for Malignant Lymphoma (Cheson et al 2007) will apply. The duration of response is defined as the time from the first documented response to the date first documented disease progression or relapse or death due to any cause. The duration of response will be summarized descriptively for each patient group.

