2.7 Analysis of secondary objective(s)

For all efficacy parameters, data will be listed, summarized, or analyzed by tumor group.

The secondary objectives for this study are as follows:

- To assess overall response rate (ORR) by RECIST 1.1 in solid tumors and by Revised Response Criteria for Malignant Lymphoma (Cheson et al 2007) in lymphoma
- To assess TTR, DOR, TTP and PFS rate at 1 and 2 years
- To assess safety and tolerability of the study drugs

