2.14 Interim analysis

Scheduled interim data reviews will occur for the primary endpoint of clinical benefit rate only as required by the Bayesian Hierarchical design. The first interim data review will be performed after the 5 subjects have CBR data available within a cohort. Interim analyses will continue every 3 months thereafter provided at least 10 subjects contribute new CBR data to the subsequent interim. At each interim analysis, the tumor cohorts will be evaluated for early futility and early success by comparing posterior quantities for the response rate to pre-specified early stopping criteria.

There is no plan for a formal interim analysis of safety or other secondary endpoints for this study. However, for publication or other purposes, interim data review of clean data will be performed as necessary. At these interim reviews, patient demographics/baseline characteristics, the primary and secondary endpoints as applicable, and all important safety endpoints will be summarized. No formal report will be issued for these data reviews.

3 Sample size calculation

The sample size was chosen by the usual criteria of obtaining adequate power for the alternative hypothesis of interest as given in Sections 6.2.2 and 6.2.3 of Appendix 4 of protocol. This hypothesis corresponds to a generally effective treatment across cohorts and incorporates variation in treatment effects to reflect the realistic expectation that treatment effects may differ by cohort. In this setting, analytical power calculations are not possible, but the design was simulated to obtain the power of the study as shown in the appendix. The sample sizes shown (minimum of 5 for futility stopping, minimum of 10 for early success and maximum of 24 as a cohort cap) achieve adequate power for the alternative hypothesis. The simulations included the expected variable accrual by simulating a Poisson process with expected accrual also shown in the appendix.

4 Change to protocol specified analyses

As per study team suggestion, the definitions of full analysis set (FAS) and safety set have been changed(defined in [section 2.2](#)).

5 Appendix

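### The SAP plans duration of response only for all tumour types combined, whereas the protocol requires a descriptive summary for each tumour cohort, and the departure is not declared

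*SAP*

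**What the plan says.** DOR is a named secondary endpoint. Protocol Table 3-1 says: "The duration of response will be summarized descriptively for each tumor cohort". Protocol 10.5.1 repeats the requirement: "The duration of response will be summarized descriptively for each patient group".

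SAP 2.7 opens its secondary analyses with a general rule: "For all efficacy parameters, data will be listed, summarized, or analyzed by tumor group". Protocol 10.5.1 carries the same rule.

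In SAP 2.7.2 the DOR paragraph provides for a Kaplan-Meier summary and a median with 95% confidence interval "only if there are sufficient numbers of events, otherwise, only listing of DOR will be provided". It then states the level of analysis: "Analyses will be based all tumor types combined". The paragraph just before it, on PFS, TTP and TTR, also starts from a combined analysis but adds: "For tumor types, separate summaries will be performed by the tumor type".

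SAP section 4, on changes to protocol-specified analyses, says only that "the definitions of full analysis set (FAS) and safety set have been changed".

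**The concern.** The study draws its conclusions cohort by cohort, and the protocol asks for durability of response at the same level. If the SAP is followed as written, a reader of the report would find response rate, PFS, TTP and TTR broken down by tumour type. The report would hold no planned DOR summary for any single cohort.

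The combined median does not replace it. It weights each cohort by the number of responders that cohort supplies, so it depends partly on which cohorts enrolled more patients and responded. It also joins responses judged by RECIST 1.1 with DLBCL responses judged by the lymphoma criteria. A change of this kind from the protocol should be visible in SAP section 4, with a reason, and it is not.

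**Working it through.** Neither document states an event count, power or precision for DOR, so there is no figure to reproduce. The check is a comparison of texts, followed by a feasibility calculation.

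**1. Level of analysis for each endpoint in SAP 2.7.2**

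| Endpoint | Combined | By tumour type |
|---|---|---|
| ORR | solid tumours combined | each haematological type (listing only if fewer than 4 patients); solid types with 10 or more patients |
| PFS, TTP, TTR | all types combined | yes, separate summaries |
| DOR | all types combined | none stated |

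DOR is the only one of these endpoints without a by-type summary. ORR keeps haematological types apart from the solid-tumour pool, and DOR does not.

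**2. Could another SAP provision restore the per-cohort summary?**

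- The SAP 2.7 rule allows data to be listed, summarised or analysed by group. A by-group listing would meet that rule but not the protocol's per-cohort summary.
- SAP 2.2.3 names tumour cohorts as a subgroup for repeating some efficacy analyses where appropriate. It is discretionary and does not name DOR.
- The swimmer plot in SAP 2.7.2 is restricted to RECIST 1.1, so DLBCL is outside it. It is not stated to be by cohort.
- SAP 2.1 lists all collected data. That preserves the information without summarising it.

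None of these commits the SAP to what the protocol asks for.

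**3. Is the change declared?** SAP section 4 names only the two analysis-set definitions. The SAP's document history does not mention DOR, and no reason for pooling is given.

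**4. What the pooled median describes.** If cohort g supplies r_g responders and has duration curve S_g(t), the pooled curve (setting censoring aside) is S(t) = Σ w_g S_g(t), with w_g = r_g / Σ r_g. The median solves S(t) = 0.5. This is well defined, but it belongs to the mixture and not to any one cohort unless the cohort curves agree.

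**5. Is a per-cohort summary feasible?** Expected responders = n × ORR. The 5% to 30% range for ORR is an assumption. Its upper end follows the protocol's selection of tumours with response rates below 30% on checkpoint monotherapy (section 1.1.2). The sizes are 10 (before expansion), 24 (the Appendix 4 cap) and 30 (the section 4.3 maximum).

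| n | ORR 5% | ORR 15% | ORR 30% |
|---|---|---|---|
| 10 | 0.5 | 1.5 | 3.0 |
| 24 | 1.2 | 3.6 | 7.2 |
| 30 | 1.5 | 4.5 | 9.0 |

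The binomial probability of at least five responders in a cohort of 24 is 0.01, 0.29 and 0.89 at those three rates. Five is only a marker, because the SAP does not define a sufficient number of events. A count with individual durations or a range is feasible wherever there are responders. A Kaplan-Meier median often will not be.

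**The case against.** The best defence is that the SAP's DOR sentence does not contain the word only. The general by-group rule in SAP 2.7 still stands, so the combined analysis could be an addition to it. That reading is possible, but the PFS, TTP and TTR paragraph weakens it: there the authors wrote out the by-type summary under the same general rule. At best the SAP is ambiguous and needs the same edit.

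The second defence is that so few responders are expected per cohort that a listing and a swimmer plot would show nearly everything. Much of this stands. The loss is of a planned summary, not of data. Still, the protocol asks only for a descriptive summary, which small numbers allow, and the SAP does not offer sparsity as its reason.

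Third, PFS, TTP and TTR are also pooled across RECIST and lymphoma criteria, so that mixing is not peculiar to DOR. This is correct. The difference is that those endpoints also have by-type summaries.

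A reader might also try to size the problem by using the historical median PFS values (1.5 to 6.2 months, Protocol Table 10-1) in place of cohort DOR medians. The documents do not support this. Those values were used to derive historical control CBRs and are not durations among responders. The protocol's own DOR figures on PD-1 blockade are 29.1 weeks in SCLC (section 1.1.2.1) and 24 weeks in gastric cancer (section 1.1.2.2), a ratio of 29.1/24 ≈ 1.2, with SCLC the longer. Table 10-1 has SCLC much the shorter, at 1.5 against 5 months. Both DOR samples were PD-L1-selected, so they do not supply a substitute size either.

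**Conclusion.** The point holds as an undeclared mismatch between protocol and SAP on a secondary endpoint. The protocol requires a per-cohort descriptive DOR summary in two places; the SAP's DOR paragraph plans a combined one and section 4 does not mention it. This rests on the text alone and needs no distributional assumption. The feasibility figures rest on the assumed response rates.

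Two stronger conclusions do not follow. A reader might infer that the pooled median has no meaning; it does have one, as a summary weighted by responder mix, but it answers a different question from the protocol's. A reader might also infer that cohort decisions are compromised. They are not: futility, expansion and final success (Protocol 10.4.3 and Appendix 4) depend only on the posterior probability for CBR, and DOR enters none of those rules. Error rates and power are unchanged. No numerical effect on DOR can be derived from the documents. The issue is worth correcting but does not threaten the primary analysis.

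**What to change.** In SAP 2.7.2, state that DOR is summarised descriptively by tumour group as in Protocol 10.5.1. Give the number of responders, the range of durations and the censoring status for each group, with a Kaplan-Meier median only where events suffice. Keep the combined analysis and label it supportive. If the sponsor prefers combined only, record that in SAP section 4 with the reason.

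The cost is a by-group run of an existing table, or a short declaration. The downside is that small-cohort summaries will be imprecise and often rest on a few responders, so they should be read as description. The latest entry in the SAP's document history falls after database lock. Because the per-cohort summary is already in the protocol, adding it restores a planned analysis and does not introduce a data-driven one.

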2.7.3 Handling of missing values/censoring/discontinuations

Handling of missing tumor assessments in ORR analysis

For the computation of ORR, in case of solid tumor all confirmed responses (CR or PR) reported up to the analysis cut-off will be included. Patients with no valid radiological assessment or unconfirmed responses will be considered as non-responders. In particular, patients with CR or PR at the last radiological assessment prior to cut-off and no response at the previous assessment are by definition unconfirmed and will be considered as non-responders for the primary analysis.

Patients with unknown or missing BOR will be counted as failures (non-responders). If there is no baseline tumor assessment, all post-baseline overall lesion responses are expected to be 'Unknown'. If no valid post-baseline tumor assessments are available, the BOR must be 'Unknown' unless progression is reported. For the computation of ORR, these patients will be included in the FAS and will be counted as 'failures'.

Censoring rules TTP and PFS calculation

If a patient has not progressed or is not known to have died due to underlying cancer or has received any further anti-neoplastic therapy in the absence of progression, at the analysis cutoff date, will be censored at the date of the last adequate tumor assessment before the cut-off date or before the start of the new anti-neoplastic therapy date, whichever is earlier. Patients who do not have any post-baseline tumor assessment will be considered as censored at Day 1.

2.8 Safety analyses

All safety analyses will be based on the safety set, and follow the definitions of on-treatment assessment/event and observation periods specified in [Section 2.1.1](#), unless otherwise specified.

2.8.1 Adverse events (AEs)

AE summaries will include all AEs occurring during on treatment period ([Section 2.1.1](#)). All AEs collected in the [Adverse Events] eCRF page will be listed along with the information collected on those AEs, e.g., AE relationship to study drug, AE outcome etc. AEs with start date outside of on-treatment period will be flagged in the listings. All deaths collected in the [Death] eCRF page will be listed along with the reason.

AEs will be summarized by number and percentage of patients having at least one AE, having at least one AE in each primary system organ class (SOC) and for each preferred term (PT)

using MedDRA coding. A patient with multiple occurrences of an AE will be counted only once in the respective AE category. A patient with multiple CTCAE grades for the same preferred term will be summarized under the maximum CTCAE grade recorded for the event.

In AE summaries, the primary system organ class will be presented alphabetically and the preferred terms will be sorted within primary SOC in descending frequency. The sort order for the preferred term will be based on their frequency in the total column.

The following AE summaries will be produced by SOC and PT (and maximum grade, as needed);

- AEs, regardless of study drug relationship
- AEs, suspected to be study drug related
- Adverse events, regardless of study drug relationship, by preferred term
- Most frequent adverse events, regardless of study drug relationship, by preferred term ($> x\%$)
- SAEs, regardless of study drug relationship
- SAEs, suspected to be study drug related
- AEs leading to study drug discontinuation, regardless of study drug relationship
- AEs requiring dose adjustment or interruption, regardless of study drug relationship

In addition, overall summary of AEs (including deaths) will be produced. Separate listing will be produced for SAEs.

AEs during on-treatment or extended safety follow-up period

AE monitoring should be continued for at least 150 days following the last administration of study drug. In addition to the treatment-emergent (on-treatment) AE summaries described above, the supportive summaries of all AEs, treatment-related AEs occurring during the on-treatment period or extended follow-up period will be produced in a similar manner.

The following AE summaries will be produced by SOC and PT (and maximum grade, as needed) for all AEs occurring during the on-treatment period or extended follow-up period;

- AEs, regardless of study drug relationship
- AEs, suspected to be study drug related
- SAEs, regardless of study drug relationship
- SAEs, suspected to be study drug related

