7.1.7 Follow up for safety evaluations

150-day safety follow up period

All patients must have safety evaluations for 30, 90 and 150 days after the last dose of study treatment. Antineoplastic therapies since discontinuation of study drug will be collected during this follow-up period. Concomitant medications will be collected until the 30-day safety follow-up has been completed or the start of a new antineoplastic therapy, whichever occurs first. Information related to AEs (including concomitant medication taken for ongoing AEs) will be collected for 150 days after the last dose of study drug. All AEs suspected to be related to study treatment should be followed up weekly or as clinically indicated until resolution or stabilization. Data collected should be added to the Adverse Events CRF, the antineoplastic therapies since discontinuation of study treatment CRF and the Concomitant Medications CRF.

For a female participant of childbearing potential, a urine pregnancy test will be performed on Day 30, 60, 90, 120 and 150 after stopping the study treatment. Please see [Section 7.2.2](#) for details

If patients refuse to return for these visits or are unable to do so, every effort should be made to contact them or a knowledgeable informant by telephone to determine if the patient had disease progression.

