8.1 Adverse events

8.1.1 Definitions and reporting

An adverse event is defined as the appearance of (or worsening of any pre-existing) undesirable sign(s), symptom(s), or medical condition(s) that occur after patient's signed informed consent has been obtained.

Abnormal laboratory values or test results occurring after informed consent constitute adverse events only if they induce clinical signs or symptoms, are considered clinically significant,

require therapy (e.g., hematologic abnormality that requires transfusion or hematological stem cell support), or require changes in study medication(s).

Adverse events that begin or worsen after informed consent should be recorded in the Adverse Events CRF. Conditions that were already present at the time of informed consent should be recorded in the Medical History page. Adverse event monitoring should be continued for at least 150 days following the last dose of study treatment. After initiation of new post-treatment antineoplastic therapy, only AEs suspected to be related to study treatment will be collected in the Adverse Events CRF. Adverse events (including lab abnormalities that constitute AEs) should be described using a diagnosis whenever possible, rather than individual underlying signs and symptoms. When a clear diagnosis cannot be identified, each sign or symptom should be reported as a separate Adverse Event.

Adverse events will be assessed according to the Common Terminology Criteria for Adverse Events (CTCAE) version 4.03

If CTCAE grading does not exist for an adverse event, the severity of mild, moderate, severe, and life-threatening, corresponding to Grades 1 - 4, will be used. CTCAE Grade 5 (death) will not be used in this study; rather, information about deaths will be collected through a Death form.

The occurrence of adverse events should be sought by non-directive questioning of the patient (subject) during the screening process after signing informed consent and at each visit during the study. Adverse events also may be detected when they are volunteered by the patient (subject) during the screening process or between visits, or through physical examination, laboratory test, or other assessments. As far as possible, each adverse event should be evaluated to determine:

- The severity grade (CTCAE Grade 1-4)
- Its duration (Start and end dates)
- Its relationship to the study treatment (Reasonable possibility that AE is related: No, Yes)

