8.2.2 SAE Reporting

For patients who sign the study ICF, SAE collection will start upon signing whether the patient is a screen failure or not.

To ensure patient safety, every SAE, regardless of suspected causality, occurring after the patient has provided informed consent and until at least 150 days after the patient has stopped study treatment must be reported to Novartis within 24 hours of learning of its occurrence. If a patient starts a post treatment antineoplastic therapy, then only SAEs suspected to be related to study treatment will be reported.

Any additional information for the SAE including complications, progression of the initial SAE, and recurrent episodes must be reported as follow-up to the original episode within 24 hours of the investigator receiving the follow-up information. An SAE occurring at a different time interval or otherwise considered completely unrelated to a previously reported one should be reported separately as a new event.

Any SAEs experienced after the 150 day safety evaluation follow-up period should only be reported to Novartis if the investigator suspects a causal relationship to the study treatment.

Information about all SAEs is collected and recorded on the Serious Adverse Event Form; all applicable sections of the form must be completed in order to provide a clinically thorough report. The investigator must assess and record the relationship of each SAE to each specific study treatment (if there is more than one study treatment), complete the SAE Form in English, and submit the completed form within 24 hours to Novartis. Detailed instructions regarding the SAE submission process and requirements for signatures are to be found in the investigator folder provided to each site

Follow-up information is submitted in the same way as the original SAE. Each re-occurrence, complication, or progression of the original event should be reported as a follow-up to that event

regardless of when it occurs. The follow-up information should describe whether the event has resolved or continues, if and how it was treated, and whether the patient continued or withdrew from study participation.

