2.2.2 Safety set

The Safety Set will include all patients who received at least one dose of study treatment.

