Additional summaries will be provided to report medications starting between 31 days after last dose of study PDR001 and 150 days after last dose of PDR001. All reported concomitant therapies will be listed. Any concomitant therapies starting and ending prior to the start of PDR001 or starting more than 150 days after the last dose of PDR001 will be flagged in the listing. The safety set will be used for all concomitant medication tables and listing.

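### The supportive all-causality AE and SAE tables to day 150 divide by the whole safety set, although unrelated events are not collected after new anticancer therapy; the day 31–150 medication table has a similar gap

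*SAP*

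**What the plan says.** **Analysis rule.** SAP 2.8 states that "All safety analyses will be based on the safety set", and SAP 2.2.2 defines it without any follow-up condition: "The Safety Set will include all patients who received at least one dose of study treatment". SAP 2.8.1 reports the number and percentage of patients with at least one event. Beside the main tables, which end 30 days after last dose (SAP 2.1.1.8), it plans supportive tables "for all AEs occurring during the on-treatment period or extended follow-up period". Their rows include "AEs, regardless of study drug relationship", and the same for SAEs. SAP 2.1.1.8 sets the horizon at 150 days after last dose. No cut at new therapy, at-risk denominator or footnote is given.

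**Collection rule.** Protocol 8.1.1: "After initiation of new post-treatment antineoplastic therapy, only AEs suspected to be related to study treatment will be collected in the Adverse Events CRF". Protocol 8.2.2: "If a patient starts a post treatment antineoplastic therapy, then only SAEs suspected to be related to study treatment will be reported".

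**Medications.** SAP 2.4.2 plans a safety-set summary of "medications starting between 31 days after last dose of study PDR001 and 150 days after last dose of PDR001". Protocol 7.1.7 says: "Concomitant medications will be collected until the 30-day safety follow-up has been completed or the start of a new antineoplastic therapy, whichever occurs first". The same section keeps medication for ongoing AEs under collection for the full 150 days.

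**A tension within the protocol.** Sections 6.3.2 and 7.1.7 describe 150 days of AE follow-up or collection for all patients and do not mention the limit after new therapy.

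**The concern.** A patient who starts new antineoplastic therapy at, say, day 45 after last dose stays in the denominator to day 150. From day 45 an unrelated event in that patient cannot enter the numerator. The row is labelled all-causality, but for that patient it becomes a related-events row partway through.

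These are the SAP's AE tables that match the 150-day window which Protocol 10.5.2 sets for safety summaries. Protocol 10.5.2 also presents safety tables by patient group. If cohorts move to the next treatment at different speeds, part of any difference between their columns may reflect collection. The reader cannot judge how much: the SAP document history removes the summary table of antineoplastic therapy after discontinuation, and SAP 2.4.2 leaves listings only.

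The medication table raises the same question. A low percentage on days 31–150 could be read as low use when it reflects restricted collection.

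**Working it through.** The plan gives no figure to reproduce: no rate of new therapy and no expected AE percentage to day 150.

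**1. Direction.** Take any all-causality row with N safety-set patients. Let A be the patients with at least one such event by day 150, and C those with at least one *collected* event. Every patient in C is in A, so C/N ≤ A/N. The gap opens only when a patient's first event for that row is unrelated and falls after the start of new therapy. For rows of suspected-related events the collection rule changes nothing.

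**2. Illustrative size, post-treatment events.** All inputs here are assumptions: p is the true 150-day risk of a first unrelated event after last dose (10–35%), f the share starting new therapy (20–60%), s the start day (30 or 60). With a constant hazard, λ = −ln(1−p)/150 and

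observed = (1−f)·p + f·(1−exp(−λs)).

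Example with p = 20%, f = 40%, s = 30: 1−exp(−30λ) = 1−0.8^0.2 = 0.0437, so observed = 0.6×0.20 + 0.4×0.0437 = 13.7%. Over the whole grid, observed/true runs from 0.53 to 0.89.

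**3. Illustrative size, cumulative tables.** The planned tables run from first dose, so a patient already counted cannot be lost. If P0 is the proportion already counted by last dose, the shortfall is (1−P0)·(p−observed). For scale, P0 is taken from the earlier combination study in Protocol 1.2.3.2: 65/186 = 34.9% with any SAE and 171/186 = 91.9% with any AE. With s = 30:

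| Row | p | Shortfall, f = 20% | Shortfall, f = 60% |
|---|---|---|---|
| Any SAE (P0 = 34.9%) | 10% | 1.0 points | 3.1 points |
| | 20% | 2.0 | 6.1 |
| | 35% | 3.5 | 10.4 |
| Any AE (P0 = 91.9%) | 10% | 0.1 | 0.4 |
| | 20% | 0.3 | 0.8 |
| | 35% | 0.4 | 1.3 |

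A preferred term that nobody has had by last dose (P0 = 0) keeps the full loss: p = 10%, f = 60%, s = 30 gives 5.25% observed, 4.7 points short.

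**4. Lost person-time, a different quantity.** Assume 12 weeks (84 days) from first to last dose, so the window is 84 + 150 = 234 days. If a share f starts new therapy on day s, the unobserved share for unrelated events is f·(150−s)/234. For (0.4, 60) it is 36/234 = 15%; for (0.6, 45), 63/234 = 27%; for (0.7, 45), 73.5/234 = 31%. These are shares of follow-up, not points of incidence.

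**5. Medications.** Set side by side, SAP 2.4.2 tabulates starts from day 31, while Protocol 7.1.7 ends general collection at the 30-day follow-up, or at new therapy if that comes first. Protocol 7.1 allows that visit to be up to 7 days late. Apart from those few days, only medication for ongoing AEs can appear.

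**The case against.** Much of the case on the other side stands.

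- The affected AE tables are called supportive. The main tables end at day 30, related-event tables are untouched by the rule, and deaths are recorded on a separate form and summarised to day 150 (SAP 2.8.2). A new therapy started within 30 days of last dose would also truncate the main all-causality tables, but only for its part of that period.
- SAP 2.1.1.8 describes the summaries as events collected up to 150 days, so a table of collected events is consistent with the protocol. That is fair, but the row labels do not say it and no footnote does.
- Cutting only the all-causality tables at new therapy would let a related count exceed the all-causality count. This is right, and the fix below allows for it.
- The latest SAP change is dated after database lock, so a new statistic would be a post-lock addition. This also stands.

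Four stronger readings are tempting, and the documents do not support them:

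- *The percentages are understated by 15–31%.* Those figures are lost person-time. With 91.9% already counted, the any-AE row could lose at most 100 − 91.9 = 8.1 points even if every remaining patient were missed.
- *The historical rates show that 49–94% of patients move on.* The rates of 51.1% and 6.25% in Protocol Appendix 4 do leave 48.9% to 93.75% without benefit at 24 weeks if the drug is inactive. But they are approximations from median PFS, which counts deaths as well as progression. Treatment beyond progression is allowed (Protocol 7.1.4), and progression by week 24 does not date new therapy relative to last dose.
- *Medications are not collected after day 30.* Protocol 7.1.7 restricts collection; it does not end it.
- *Cohorts cannot be compared.* Safety analyses are descriptive, without testing (SAP 2.1). Unequal truncation could confound an informal comparison, but the documents do not show that it occurs.

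**Conclusion.** The mismatch between collection and tabulation is real, and its direction is certain: the all-causality AE and SAE percentages to day 150 can only equal or fall below the true incidence. The size is unknown, because it depends on how many patients start new therapy and when. Under the assumed inputs, with new therapy at day 30, it is 0.1 to 1.3 points for any AE and 1.0 to 10.4 points for any SAE; these figures also borrow P0 from another study and assume a constant hazard. Single preferred terms can lose a larger fraction of their value. The day 31–150 medication table shows a restricted subset under a general description.

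Severity is minor: the AE tables are supportive, and neither the primary endpoint nor the related-event tables are touched. It is still worth correcting, because the remedy uses data already held.

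**What to change.** 1. **SAP 2.8.1.** Keep the crude all-causality AE and SAE tables to day 150, with a footnote stating the collection rule and the number of patients who started new therapy within the window. Add a version that counts events before new antineoplastic therapy, with person-time at risk ending at the earliest of new therapy, death, loss to follow-up or day 150. Show related events on the same cut beside it, so that the two counts are comparable. Leave the planned related-event tables to day 150 as they are.
2. **SAP 2.4.2.** Restrict the day 31–150 medication table to medications taken for adverse events and title it so, or drop it.
3. **Protocol.** Reconcile the unqualified 150-day AE follow-up in 6.3.2 and 7.1.7 with the limits in 8.1.1 and 8.2.2.

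**Cost.** One derived end-of-collection date and a few extra supportive outputs. Protocol 7.1.7 already collects antineoplastic therapies after discontinuation, and SAP 2.7.3 already uses their start date to censor TTP and PFS. Outputs added now should be labelled as added after database lock.
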